15. CLINICAL CENTERS

16. DATA HANDLING

17. DATA ANALYSIS

REFERENCES

APPENDICES

PROTOCOL SUMMARY

Title:	Real-time electrogram Analysis for Drivers of AtRial fibrillation (RADAR)
Objective:	This study will assess the ability of real time electrogram processing to identify driver domains to target for ablation in persistent AF patients
Design:	This is a prospective, multi-center, non-randomized, un-blinded, observational trial.
Enrollment:	
Eligible subjects will be consented for participation in the trial prior to undergoing AF ablation. Patients are considered eligible if they have
 
 1. ≥ 18 years of age. 2. Symptomatic or drug-refractory patients who are planned to undergo a catheter ablation procedure for persistent AF (either a first procedure or a redo procedure). Patients may have either persistent AF (AF > 7 days) or long-standing persistent AF (AF > 1 year's duration). 3. Ability to understand the requirements of the study and sign the informed consent form. 4. Willingness to adhere to study restrictions and comply with all post-procedural follow-up requirements 5. Projected lifespan greater than 1 year. 
Patients will be excluded from the trial if:
 
 1. Rheumatic heart disease, 2. Current intra-cardiac thrombus, 3. History of MI or CABG within 6 weeks 4. Unstable angina 5. CVA or TIA within 3 months 6. Contraindication to anticoagulation 7. Class IV HF; 8. Unable to sign consent 9. Projected lifespan of < 1 year 10. Women known to be pregnant or to have positive beta-HCG. 11. Participation in another study that would interfere with this study. 
Patients are considered enrolled once consented. Patients who do not undergo AF ablation within 90 days of enrolling will be considered to be screen failures.
 
Sixty-five subjects are expected to be enrolled in the study.

Clinical Sites:	
 1. Mount Sinai Hospital, New York, NY 2. University of Colorado Hospital, Denver, CO 3. University of Kansas Medical Center, Kansas City, KS 4. Seton Medical Center, Austin, TX 5. Porter Adventist Hospital, Denver, CO 6. Massachusetts General Hospital, Boston, MA
Time Course:	Expected duration of patient enrollment is approximately 8 months to 1 year.
Subject Description:	Subjects will only be eligible for this study if they are ≥ 18 years of age and have a history or suspected history of AF
Primary Endpoints:	
 1. Acute Procedural Outcome Analysis: after performing procedures on the 65 patients 2. Clinical Outcome Analysis - Freedom from recurrent AF after one

	
procedure at 12 months.
 
3. Clinical Outcome Analysis – Freedom of recurrent AF after two procedures at 12 months.

Additional Endpoints:	
1. Clinical Outcome Analysis – Freedom from recurrent AT after one procedure at 12 months.
 
2. Clinical Outcome Analysis – Freedom from recurrent AT after two procedures at 12 months.
 
3. Total duration of RF ablation/Fluoro time/exposure/ procedure time
 
4. Procedure-related adverse events
 
5. Major Adverse Cardiac Events (MACE)
 
6. Serious Adverse Events

Follow-Up	
1. Post-Ablation blanking period = 3 months
 
2. AAD use during blanking: Any AAD is permitted, but should be stopped by 8 weeks post-procedure.
 
3. Any documented post-blanking AF episode > 30 seconds would be considered as a failure
 
4. Patients will undergo continuous 7-14 day ambulatory monitoring at 3, 6 and 12 months
 
5. A second ablation procedure using the CMA software is allowed should a patient have recurrence of AF at any time during the 1 year follow-up period.

Principal Investigator:	
[name] , M.D. Icahn School of Medicine at Mount Sinai [name]

Site, Monitoring, and Data Management Center	
Electrophysiology Clinical Research Group Icahn School of Medicine at Mount Sinai [name]

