6 ENDPOINTS

6.1 Primary Endpoint

Primary Endpoints:	
1. Acute Procedural Outcomes as defined by termination of Atrial Fibrillation into NSR or AT > 5min.2. Clinical Outcome Analysis - Freedom from recurrent AF after one procedure at 12 months.3. Clinical outcome Analysis – Freedom from recurrent AF after two procedures at 12 months.
Additional Endpoints:	
1. Clinical outcome Analysis – Freedom from recurrent AT after one procedure at 12 months.2. Clinical outcome Analysis – Freedom from recurrent AT after two procedures at 12 months.3. Total duration of RF ablation/Fluoro time/exposure/procedure time4. Procedure-related adverse events5. Major Adverse Cardiac Events (MACE)6. Serious Adverse Events

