8 SAMPLE SIZE

This safety and efficacy study will enroll 65 patients across 1-5 US centers and 1-2 OUS centers. This number has been determined on the basis of study feasibility and not by statistical means. This is a feasibility study of the mapping system performance in which the sample size of the clinical investigation is intended to provide preliminary estimates of safety and performance.

The study will involve two cohorts. The first cohort will be composed of patients with persistent AF > 7 days but < 1 year's duration. The second cohort will be composed of up to 15 patients with long-standing persistent AF (AF > 1 year's duration).

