9 PATIENT ENROLLMENT AND WITHDRAWAL

Patients meeting the study inclusion criteria will be identified in the outpatient or inpatient setting by investigators. Patients will be followed by one of the study site principal or co-investigators.

The study will typically be described (including the risks and benefits) during the initial clinic or hospital visit. Consent will typically be obtained at the time of the initial assessment if it is clear that the patient truly understands the nature of the study. Alternatively, the patient will be encouraged to take a copy of the consent form home to contemplate whether he/she would like to be enrolled in the study. Only patients who voluntarily provide consent will be included in this study. Consent will be obtained prior to undergoing the ablation procedure. Patients will be able to withdraw from the study at any point without compromising their medical care. All data will be de-identified and protected in accordance with institutional and HIPAA guidelines, including 1) de-identification of all geographic subdivisions smaller than a state; 2) all elements of dates related to the individual; 3) telephone and fax numbers; 4) email addresses; 5) social security number, medical record, health plan beneficiary, account, and certificate/license numbers; 6) vehicle identifiers; 7) device identifiers; 8) URLs and IP addresses; 9) biometric identifiers; and 10) photographic images.

[figure not shown]
Eligible subjects will be consented for participation in the trial prior to undergoing AF ablation. Patients are considered enrolled once consented. Patients will be followed for 12 months. Patients who do not undergo an ablation procedure within 90 days of enrolling will be considered to be screen failures. Additionally, if a patient does not have any ablation performed that is a result of the mapping completed by the CMA software, the patient will be considered a screen failure. Patients who are deemed to be screen failures may be considered for re-enrollment should they require a later AF ablation procedure.

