9.1 MAPPING COHORTS

In the first cohort of up to 15 patients, AF mapping (utilizing CMA) will be performed but will not be utilized to guide the ablation procedure. That is, ablation will be based on standard approaches only. The purpose of this initial cohort is to validate the software and mapping procedure. Brief operator learning curve relating to the mapping procedure is expected. Proper sampling is necessary in order to achieve full spatial coverage of an entire chamber. The benefit of the technology includes infinite spatial resolution with unlimited multiple synchronized sample locations throughout the atria, but that unlimited sampling must be balanced with time added to the procedure for sampling and software computation. The first cohort of patients is designed to allow for this learning curve to be normalized between the catheter operators and the software operators. Performing the mapping alone, Kurian T, et al. have seen no procedure related adverse events in over 61 patients. As such, it is safe and worthwhile to take an initial cohort of patients to normalize the mapping process in persistent AF patients where the chambers are often diseased, complex and dilated requiring operator skill to

sample an entire chamber appropriately. The consistent convergence of the CMA software within five minutes signifies that a balance has been struck between the amount of sampling data supplied to the software and the operator's satisfaction in adequate sampling of the patient's anatomy. Over the course of these cases, if the software algorithm is converging to a solution consistently within five minutes of processing time, the size of this validation cohort may be reduced to less than 15.

In the second cohort of patients (potentially patients 16-65), AF mapping (utilizing CMA) will be performed and used to point the operator to regions within a heart chamber that should be interrogated further for suspicious electrogram activity, as measured by the St. Jude Ensite System, and ablated if the suspicious electrogram activity persists.

➤ **Empiric ablation (CFAE or linear ablation) is not permitted**

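### The 65 counts consents, no primary endpoint has a stated analysis population, and the screen-failure rule read literally removes every run-in patient; the guided cohort is 50 if the run-in is 15.

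*Combined protocol and SAP*

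**What the plan says.** **Enrolment.** The Protocol Summary (Enrollment) gives the target as "Sixty-five subjects are expected to be enrolled in the study" and fixes the moment of enrolment: "Patients are considered enrolled once consented". Section 9 repeats that definition. Section 8 says of the 65: "This number has been determined on the basis of study feasibility and not by statistical means".

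**Acute primary endpoint.** The summary describes it as "Acute Procedural Outcome Analysis: after performing procedures on the 65 patients". Section 6.1 gives the event, "Acute Procedural Outcomes as defined by termination of Atrial Fibrillation into NSR or AT > 5min", without a denominator.

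**Analysis.** Section 17 calculates percentages on non-missing observations. It names no analysis population for any endpoint.

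**Screen failures.** Section 9 has two rules that act after consent. One covers patients not ablated within 90 days. The other applies "if a patient does not have any ablation performed that is a result of the mapping completed by the CMA software". Screen failures may be re-enrolled for a later ablation, but the text does not say whether they are replaced or whether they count towards 65.

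**Run-in.** Section 9.1 says that in a first cohort of up to 15 patients "AF mapping (utilizing CMA) will be performed but will not be utilized to guide the ablation procedure". This cohort may be made smaller than 15. The guided cohort is given as potentially patients 16 to 65.

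**The concern.** Three different groups could be meant by the 65: those who consent, those who undergo a procedure, and those whose ablation is guided by the map. The plan moves between them without saying which one carries each estimate. In a single-arm study whose stated aim is preliminary estimates of safety and performance, the denominator is a large part of the result.

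Two consequences follow. If all treated patients are pooled, the estimate mixes patients ablated with the map and patients ablated without it. If the second screen-failure rule is applied as written, treated patients leave after the fact, for a reason that arises during the procedure being evaluated.

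**Working it through.** **1. The stated 65.** Section 8 sets it by feasibility. No power, effect size, precision target or dropout rate is given, so there is no formula to reproduce. What can be checked is the split.

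**2. The guided cohort** (sections 8 and 9.1). Patients 16 to 65 inclusive: 65 − 16 + 1 = 50, which agrees with 65 − 15 = 50. Because 15 is the largest run-in allowed, the general form is guided = 65 − run-in:

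| Run-in | Guided, before screen failures |
|---|---|
| 15 | 65 − 15 = 50 |
| 10 | 65 − 10 = 55 |
| 5 | 65 − 5 = 60 |

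The 15 used here is the mapping run-in of section 9.1. Section 8 has a separate cohort of up to 15, those with long-standing persistent AF, which is a different division of the same 65.

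**3. Consents against procedures.** Any consented patient not ablated within 90 days is one of the 65 who has no study procedure. A single such loss makes the summary's description of the acute endpoint untrue unless that patient is replaced, and no replacement rule is stated. The numbering in section 13.1, which stops at 065 for screening and enrolment together, fits the reading that screen failures use up places. It does not settle the matter.

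**4. Section 9 against section 9.1.** Section 9 makes a patient with no map-derived ablation a screen failure and gives no exemption. Section 9.1 requires that run-in ablation not use the map. Every run-in patient therefore meets the screen-failure condition by design, yet section 9.1 counts the run-in inside the 65. Both cannot hold as written.

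**5. The same rule in the guided cohort.** All patients receive pulmonary vein isolation (section 10.3). Ablation of a mapped region depends on the operator finding that suspicious electrograms persist there (section 9.1), and section 10.3 foresees that no drivers may be found. Such a patient has been treated and has an acute outcome, but is a screen failure under section 9. An illustration with assumed figures: 50 guided patients, 30 terminations (60.0%), and 10% (5 patients) without map-directed ablation.
- If all 5 stayed in AF, dropping them gives 30/45 = 66.7%.
- If all 5 terminated, dropping them gives 25/45 = 55.6%.

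The reported rate moves in either direction, depending on who is dropped.

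**6. Precision, for illustration.** These are Clopper-Pearson 95% intervals near 59%, the freedom from AF that section 3 cites for pulmonary vein isolation alone at 18 months:
- n = 65: 38/65, 45.6% to 70.6%, half-width 12.5 points.
- n = 60: 35/60, 44.9% to 70.9%, half-width 13.0 points.
- n = 55: 32/55, 44.1% to 71.3%, half-width 13.6 points.
- n = 50: 30/50, 45.2% to 73.6%, half-width 14.2 points.

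**The case against.** The best defence is that this is a declared feasibility study. Section 8 claims no power or precision, and section 9.1 states the split between run-in and guided patients openly. The summary's phrase about the 65 can be read as saying when the acute analysis takes place. All of that stands. No stated precision or power is missed, and the phrase is loose wording for an endpoint whose definition in section 6.1 carries no number.

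The defence does not reach the conflict between sections 9 and 9.1, the missing denominators, or the silence on replacement.

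A reader might also infer two stronger things that the documents do not support.
- *That the guided cohort cannot exceed 50.* Section 9.1 lets the run-in shrink, so 50 belongs to a full run-in of 15.
- *That only some 33 to 39 guided patients will remain.* This applies the usable-data fractions in section 3 to 50: 50 × 40/61 = 32.8 and 50 × 55/70 = 39.3. Section 3 attributes the unusable data in the 70-patient series to initial tuning of the algorithms, and the run-in is there to settle the mapping process. An unusable dataset is also not the same event as having no map-derived ablation. The screen-failure rate is simply not given.

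**Conclusion.** The point holds as a fault in the definition of the analysis population. On the documents' own figures, guided estimates rest on 50 of the 65 if the run-in is 15 (50/65 = 77%), and on more if it is shortened. That is before unquantified screen failures and assumes that these are not replaced. The illustrative loss of precision from 65 to 50 is modest: 14.2 − 12.5 = 1.7 points of half-width. It concerns a 12-month type of rate; the documents give no expected rate for acute termination.

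The more serious part needs no assumed rate. Section 9 contradicts section 9.1 for every run-in patient, and it lets events during the procedure decide which guided patients are counted. This takes screen failure in its ordinary sense of removal from the analysis, which the plan does not spell out.

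**What to change.** 1. Reconcile sections 9 and 9.1 by exempting run-in patients from the screen-failure rule on map-derived ablation.
2. Define the acute endpoint's denominator as all patients who undergo the study procedure. Keep guided patients who had no map-directed ablation in that analysis. Report run-in and guided patients separately, with the guided cohort carrying the performance estimate. Name the denominator for the two 12-month primary endpoints as well.
3. In the Protocol Summary and section 8, restate 65 as consents, with 50 guided if the run-in is 15 (more if it is shortened), before screen failures. Say whether screen failures are replaced and how re-enrolled patients count.

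No extra patients are needed. The cost is wording in the Protocol Summary and sections 6.1, 8, 9 and 17, and a smaller number visibly behind the guided estimate.

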2 STUDY OBJECTIVE

This prospective, multicenter observational study will examine the ability of real time electrogram processing mapping to identify driver domains to target for ablation in persistent AF patients.

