Extensive retrospective evaluation of CMA has been performed and published^{3,4}. A total of 70 patients have been mapped using CMA at Mercy Hospital in St. Louis, MO, University of Kansas Medical Center in Kansas City, KS, and Mount Sinai Hospital in New York, NY. No adverse events were associated with the mapping process. Fifty-five of the 70 mapped patients produced analysis that was usable. The unusable patient data can be attributed to initial tuning of the signal processing algorithms. In this 55 patient series of data, patients were mapped using CMA and subsequently ablated with standard of care ablation at the operator’s discretion, without the benefit of the CMA generated maps. Ablation techniques included Wide Area Circumferential Ablation (WACA), empiric Complex Fractionated Atrial Electrogram (CFAE) Ablation and empiric linear lesion Ablation. Retrospectively, the data was analyzed to see the effects of incidental ablation of CMA identified AF Driver domains. Ultimately, the use of CMA generated maps of AF driver domains may serve to reduce the amount of empiric CFAE and linear lesion ablation and improve outcomes in persistent AF patients.

The Abstract and Conclusion sections from the journal article entitled “***Characterization of Drivers in Patients with Persistent Atrial Fibrillation to Identify Substrate Based Rotor Ablation Targets***” serve as a good overview of CMA and associated retrospective clinical findings:

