ABSTRACT: Recent clinical trials have shown that targeting rotors and focal impulses (FIs) during atrial fibrillation (AF) ablation improves outcomes. This study evaluated whether a novel computational mapping algorithm (CMA) could identify FIs and rotors, and characterize rotors when incidental ablation resulted in rhythm changes. Three-dimensional (3D) left atrial electroanatomic maps were created from signals recorded from multipolar circular mapping catheters in 61 patients undergoing persistent AF ablation. Forty of 61 acquired patient datasets were of adequate quality for analysis CMA, employing an AF pattern recognition algorithm, creating 3D panoramic AF maps identifying drivers of AF (FI and rotors) post procedure. Rotors were further classified as substrate (SBR) or non-substrate based (NSBR) on the basis of rotor stability, proximity to voltage transition zones and complex fractionated atrial electrograms (CFAEs). Incidentally ablated identified AF drivers, including SBRs and NSBRs, were evaluated for rhythm changes. A total of 172 drivers were identified in 40 patients (4.3 ± 2.2 drivers/patient). Seventy percent were rotors (120/172) and 30% were FIs (52/172). Sixty-seven percent of rotors were classified as SBR vs 33% as NSBR. Incidental ablation of SBRs resulted in rhythm change 91% of the time versus only 24% of the time for NSBR ($p < 0.0001$).

CONCLUSIONS: Incidental ablation of SBRs resulted in rhythm change significantly more frequently than ablation of NSBRs. Identification of drivers and classification of rotors based on substrate properties may allow a more tailored ablation approach in patients with persistent AF.

The following is a description of what each Mapping System will perform during Persistent Atrial Fibrillation cases:

St. Jude Ensite System:

1. Tracking the position of the catheters as they travel through the heart and displaying them on a screen in 3D so that X-Ray is not needed (or reduced).
2. Create a shell of the heart chamber and display on a screen so that the physician knows where the catheters are in relation to the anatomy (shell of heart chamber).
3. Display electrogram signals from all the electrodes on the different catheters in the heart.

These three features will be used for the entire case to determine where to ablate tissue.

AFTx System:

1. Receive the heart chamber shell from St Jude Ensite.
2. Receive the electrogram signals from St Jude Ensite.

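### No endpoint directly measures mapping performance, which is the study's stated objective; AF termination is only an indirect proxy, and mapping failures leave its denominator

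*Combined protocol and SAP*

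**What the plan says.** **Purpose.** Section 2 gives one objective, to "examine the ability of real time electrogram processing mapping to identify driver domains to target for ablation in persistent AF patients"; the Protocol Summary states the same aim. Section 8 describes a "feasibility study of the mapping system performance" that should yield early estimates of safety and performance, and says of the 65 patients: "This number has been determined on the basis of study feasibility and not by statistical means". Section 17 presents the study as a proof of concept for the mapping system, analysed descriptively.

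**Endpoints.** Section 6.1 lists three primary endpoints. The first is "Acute Procedural Outcomes as defined by termination of Atrial Fibrillation into NSR or AT > 5min". The second is "Freedom from recurrent AF after one procedure at 12 months", and the third is the same outcome after two procedures. The additional endpoints are freedom from AT after one and two procedures, "Total duration of RF ablation/Fluoro time/exposure/procedure time", procedure-related adverse events, MACE and serious adverse events.

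**Rules that bear on mapping.** Section 10.3 starts every patient's lesion set with pulmonary vein isolation. Section 9.1 has a first mapping cohort of up to 15 patients who are mapped but ablated without use of the map. That cohort may be shortened if the software consistently converges within five minutes. Section 9 classes a patient with no ablation resulting from the CMA map as a screen failure.

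**Earlier experience.** Section 3 reports two usability figures: "Fifty-five of the 70 mapped patients produced analysis that was usable" and, in the reproduced abstract, "Forty of 61 acquired patient datasets were of adequate quality for analysis". It attributes the losses in the 70-patient series to initial tuning of the signal processing.

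**The concern.** A feasibility study should have at least one endpoint that is the feasibility question. Here safety has endpoints and mapping performance has none. The report could therefore meet every listed endpoint without saying how often the software produced a map an operator could use.

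The rhythm endpoints do not fill the gap cleanly. In a single arm where every patient has pulmonary vein isolation, termination of AF or freedom from AF at 12 months can follow from the isolation, from ablation at mapped sites, or from both. The screen-failure rule makes this worse. A failed or empty map is the most informative negative result for this objective, and the patient who has one is reclassified out of the study.

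**Working it through.** **1. Reproducing the plan's figure.** There is nothing to reproduce. Section 8 says 65 was not derived statistically, and no alpha, power or effect size is given. The check is a comparison of objective with endpoints, followed by arithmetic for scale.

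**2. Objective against endpoints.**

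| Listed in Section 6.1 | Level | Measures the map? |
|---|---|---|
| AF termination | Patient, whole procedure | Indirectly |
| AF freedom at 12 months, one or two procedures | Patient, long term | No |
| AT freedom at 12 months, one or two procedures | Patient, long term | No |
| RF, fluoroscopy and procedure times | Procedure | No; burden only |
| Procedure-related events, MACE, SAEs | Patient, safety | No |

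The only mapping-performance criterion in the plan is convergence within five minutes (Section 9.1). It serves only to decide whether the first cohort can be shortened, and Section 17 plans no analysis of it.

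**3. How good a proxy is AF termination?**
- Section 10.3 puts vein isolation first in all patients, and the endpoint does not tie termination to a driver lesion.
- In up to 15 patients the map does not guide ablation, so their terminations say nothing about map-guided ablation.
- There is no comparator.
- Under Section 9, patients without map-directed ablation become screen failures. Section 10.3 itself foresees cases in which no driver is localized. Among those who stay, map-directed ablation is 100% by construction. Read literally, the rule also removes the whole unguided first cohort.

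**4. Earlier usable rates**, with exact (Clopper-Pearson) limits: lower = Beta(0.025; x, n − x + 1), upper = Beta(0.975; x + 1, n − x).
- 55/70 = 78.6%, 95% CI 67.1% to 87.5%
- 40/61 = 65.6%, 95% CI 52.3% to 77.3%

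**5. If those rates recurred (assumption).**
- 65 × 55/70 ≈ 51 usable, so 65 − 51 = 14 without a usable map.
- 65 × 40/61 ≈ 43 usable, so 65 − 43 = 22 without.
- With a full first cohort, 65 − 15 = 50 patients are map-guided. The same rates give about 39 and 33 usable, hence 11 to 17 without.

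**6. What the study could estimate.**

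| Usable / mapped | Exact 95% CI | Half-width (points) |
|---|---|---|
| 51/65 | 66.5% to 87.7% | 10.6 |
| 43/65 | 53.4% to 77.4% | 12.0 |
| 39/50 | 64.0% to 88.5% | about 12 |
| 33/50 | 51.2% to 78.8% | about 14 |

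**7. Effect of the dropped patients on the proxy.** Suppose, purely for illustration, that AF terminates in 50% of patients who do have map-directed ablation, and count dropped patients as not terminated. Over all patients mapped for guidance the rate is 0.50 × 0.656 = 33% to 0.50 × 0.786 = 39%. With 30% it is 20% to 24%; with 70%, 46% to 55%. Some dropped patients might terminate during vein isolation, so these figures show direction and scale only.

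**The case against.** A reader might infer that the trial cannot answer its own question at all, or that it will report nothing on mapping. The documents do not support either reading.

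- AF termination is a functional test of whether mapped sites matter, and it follows the protocol's own logic: the abstract in Section 3 uses rhythm change after ablation at driver sites as its evidence (91% against 24% for the two rotor classes). This stands as far as it goes. That evidence was tied to specific sites, however, whereas the endpoint covers the whole procedure.
- Empiric CFAE and linear ablation are forbidden, so in map-guided patients what follows vein isolation is driver ablation and then ablation of any organized AT. Redo patients are eligible and may arrive with veins already isolated. Both facts narrow the attribution problem. They do not remove it, because termination is not recorded by stage.
- Section 9.1 has a validation cohort with a convergence criterion. Section 17 says procedural characteristics will be collected and analysed and missing values counted. The CRF is not in the documents and may already capture map data. So the accurate statement is that mapping performance is not a prespecified endpoint.
- Section 3 attributes the unusable data in the 70-patient series to early algorithm tuning, so yield may now be better. That is reasonable, but it is a hypothesis this study is placed to test.
- The abstract describes left atrial maps with drivers identified after the procedure, whereas this study maps both atria in real time. The documents also do not say whether the 70- and 61-patient series overlap. The rates should therefore be neither pooled nor read as two independent forecasts.

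**Conclusion.** The concern holds in this form: no primary or additional endpoint directly measures mapping performance, although Sections 2, 8 and 17 all make it the purpose of the study. AF termination answers the objective only indirectly, and the screen-failure rule takes mapping failures out of its denominator.

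On the earlier rates, about 14 to 22 of 65 mapped patients would have no usable map and no listed endpoint would show it. This rests on two assumptions: that the earlier rates carry over, and that screen failures are left out of the analysis. The second is the ordinary meaning of the term, but Section 17 defines no analysis set.

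No stated figure in the plan is wrong. The gap is structural and should be closed before analysis. Because the study is descriptive, with no alpha or power to protect, closing it disturbs nothing else.

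**What to change.** 1. Add a descriptive feasibility endpoint to Section 6.1: the proportion of all mapped patients with a usable map, with an exact 95% CI. The denominator includes the validation cohort and mapping-related screen failures.
2. Define usable in advance. The protocol's own criterion, convergence within five minutes, is one available choice.
3. Add as secondary, in all mapped patients: drivers identified per patient.
4. Add as secondary, in the map-guided cohort only: the share of flagged sites confirmed on electrogram review and ablated, and AF termination recorded by stage (during vein isolation, or during ablation at a flagged site). These cannot be obtained as described in the first cohort, where the map does not direct ablation.
5. State in Section 17 that a failed map counts as a failure. Percentages there use non-missing observations, so a failed map entered as missing would otherwise drop out again.

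A usable map is not proof that the flagged sites are drivers. Items 1 to 3 describe yield, and item 4 gives the partial evidence on validity.

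The cost is a written usability criterion, a few CRF fields if they are not already there, and SAP wording. The changes in themselves call for no extra patients, visits or procedures. The downside for the sponsor is that an unfavourable yield would be reported openly.
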